3.1.2 Randomization Phase

The Randomization Phase portion of the study will follow a randomized, double-blind design. Ibrutinib and venetoclax/placebo will be administered using the Ramp-up Schedule that was determined to be appropriate for each TLS risk category. The Data Monitoring Committee (DMC) will review the safety recommendations made by the SRC and will be responsible for giving recommendations on continuing, modifying, or stopping the Randomization Phase of the trial (Figure 8).

Subject eligibility will be determined up to 28 days prior to randomization. Approximately 260 eligible subjects will be randomized at a 1:1 ratio to ibrutinib and venetoclax or ibrutinib and

placebo. Randomization will be stratified by number of prior lines of therapy, ECOG PS, and by TLS risk category.

Figure 8. Randomization Phase Schematic

Initially, subjects at increased risk of TLS will be hospitalized for a minimum of 24 hours (and up to 48 hours at the discretion of the investigator) at the start of the 20 mg ramp-up dose and again at the start of the 50 mg ramp-up dose of venetoclax for monitoring and prophylaxis of TLS. The DMC will review unblinded safety data during the course of the study to determine whether continued hospitalization of these subjects during ramp-up remains warranted.

Subjects will be treated with either ibrutinib and venetoclax or ibrutinib and placebo for approximately 104 weeks, followed by ibrutinib monotherapy until PD, unacceptable toxicity or withdrawal of consent. Venetoclax/placebo will be discontinued after 104 weeks of treatment regardless of response assessment.

Subjects who discontinue study treatment for any reason will be followed for progression (if not progressed before treatment discontinuation), subsequent anti-cancer therapy, and survival status until study closure.

[figure not shown]

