3.1.3 Treatment-naive Open-label Arm

In the treatment-naive open-label arm, approximately 75 subjects will be enrolled and treated with ibrutinib 560 mg and venetoclax 400 mg. Among them, approximately 50 subjects ≥ 65 years and approximately 25 subjects with a TP53 mutation will be enrolled (Figure 9).

[figure not shown]
Figure 9. Study Design: Treatment-naive Open-label Arm

w/o = without; PD = progressive disease; WC = withdrawal of consent

Ibrutinib and venetoclax will be administered using the 5-week ramp-up schedule shown in Figure 10. Treatment-naive MCL patients will use the same dose and schedule as established in the Safety Run-in for the Randomization Phase of the study. Therefore, there will be no Safety Run-in for the treatment-naive cohort. *Note: Sponsor may hold enrollment for patients in the treatment-naive open-label arm to ensure that at least 25 patients with a TP53 mutation are enrolled.*

Figure 10. Venetoclax Standard Ramp-up Schedule

Subject eligibility will be determined up to 28 days prior to first dose of study treatment.

Subjects in the protocol-defined increased-risk for tumor lysis syndrome (TLS) group will be hospitalized for a minimum of 24 hours (and up to 48 hours at the discretion of the investigator) at the start of the 20 mg and 50 mg ramp-up dose of venetoclax for monitoring and prophylaxis of TLS; subjects in the low-risk for TLS group may be hospitalized at the discretion of the investigator.

Subjects will be treated with ibrutinib and venetoclax for approximately 104 weeks (2 years), followed by ibrutinib monotherapy until PD, unacceptable toxicity or withdrawal of consent or study closure. Venetoclax will be discontinued after 104 weeks (2 years) of treatment, regardless of response assessment.

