Post-dose: For hospitalized subjects, monitor blood chemistries 4, 8, 12, 24 and, as needed, 48 hours after the venetoclax dose. For outpatient subjects, monitor blood chemistries at 6-8 hours and at 24 hours after the venetoclax dose. Electrolyte abnormalities should be corrected promptly (see Appendix H for Recommendations for Initial Management of Electrolyte Abnormalities and Prevention of Tumor Lysis). The next dose of venetoclax should not be administered until the 24-hour blood chemistry results have been evaluated. The same monitoring schedule should be followed when starting each subsequent ramp-up dose.

Hospitalization: Based on investigator assessment, subjects with high tumor burden (at least one lesion > 10 cm; or at least one lesion > 5 cm and circulating lymphocytes > 25,000 cells/mm³) and/or CrCl < 60 mL/min, are at greater risk of TLS and require hospitalization the first 24-48 hours of treatment at the 20 mg and the 50 mg ramp-up doses of venetoclax for more intensive prophylaxis and monitoring. Consider hospitalization for subsequent ramp-up doses based on reassessment of risk. During the course of the study, the DMC will review unblinded TLS data to determine whether continued hospitalization of these subjects is warranted.

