7.1.1.10 Tumor Lysis Syndrome (TLS) Risk Assessment

At Screening, all study subjects will be assessed for risk of developing TLS. The risk of TLS is a continuum based on multiple factors, including comorbidities. Subjects at increased risk are defined as having at least one lesion > 10 cm; or at least one lesion > 5 cm and circulating lymphocytes > 25,000 cells/mm³ and/or have reduced renal function CrCl < 60 mL/min. The risk may decrease as tumor burden decreases with venetoclax treatment.

Blood chemistry (creatinine, uric acid, potassium, phosphorus, calcium, and albumin if available) assessments will be performed in all subjects within 72 hours prior to initiating venetoclax treatment.

Subjects with high tumor burden at baseline and/or CrCl < 60 mL/min will be hospitalized during the first 24-48 hours of treatment at the 20 mg (Week 1) and the 50 mg (Week 2) venetoclax dose. Blood chemistry (creatinine, uric acid, potassium, phosphorus, calcium, and albumin if available) should be monitored pre-dose and 4 ± 1 , 8 ± 1 , 12 ± 1 , 24 ± 2 and, as needed, 48 ± 2 hours after the venetoclax dose. (Hospitalization for subjects lacking immediate access to a

facility capable of correcting TLS promptly or for subjects who are otherwise considered at risk for TLS should be discussed with the medical monitor). For all other subjects, blood chemistry will be monitored pre-dose, 6-8 and 24±2 hours after the venetoclax dose at the 20 mg and the 50 mg dose levels.

During the remaining ramp-up weeks (weeks 3-5), for subjects at increased risk for TLS at baseline, blood chemistries will be monitored at pre-dose and 6-8 hours after each dose increase.

Appropriate venetoclax dosing and management of subjects throughout their study treatment is guided by their individual risk for developing TLS. Risk-based TLS prophylaxis and management measures are described in Section 5.3.2.2.

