8.2 Treatment Phase

Following completion of the Screening Visit and once eligibility has been confirmed (per inclusion/exclusion criteria), subjects will initiate study treatment (see Section 5.2 for ibrutinib and venetoclax dosing).

Refer to the Schedule of Assessments (Appendix A and Appendix B) for a complete list of procedures to be performed at each scheduled study visit.

8.2.1 Treatment Visits for Standard Ramp-up Schedule for SRI, Randomization Phase, and Treatment-naive (TN) Open-label Arm

8.2.1.1 Week 1 Day 1 and Week 2 Day 1

Pre-dose (within 72 hours prior to the first venetoclax dose and before each dose increase)

- Confirmation of eligibility (per inclusion/exclusion criteria) at week 1 only.
- Update medical history at week 1 only
- AEs
- Concomitant medications (including chemotherapy, radiation, over-the-counter drugs, vitamins, and herbs)
- Physical examination
- Vital signs
- ECOG PS (Week 1 Day 1 only)
- PRO at week 1 only
- Determination of Medical Resource Utilization (MRU)
- TLS risk assessment and prophylaxis
- Hospitalization of subjects with high tumor burden
- Laboratory Tests
 - Hematology
 - Blood chemistry
 - Serum or urine pregnancy test (for women of childbearing potential only)
 (Week 1 Day 1 only)
 - o MRD peripheral blood (Week 1 Day 1 only)
 - o Biomarker blood sample (Week 1 Day 1 only)
 - o Buccal Swab (Week 1 Day 1 only)

Dosing – Week 1 Day 1 and Week 2 Day 1

The dose of venetoclax or placebo should not be administered until the blood chemistry results have been evaluated.

- In-clinic administration of venetoclax or placebo with a meal
- In-clinic administration of ibrutinib

Post-dose

- For hospitalized subjects, serum creatinine, uric acid, potassium, phosphorus, calcium, and albumin, if available should be monitored at 4±1, 8±1, 12±1 hours, after the venetoclax/placebo dose.
- For all outpatient subjects, serum creatinine, uric acid, potassium, phosphorus, calcium, and albumin, if available should be monitored at 6-8 hours after the venetoclax/placebo dose.
- Any changes in these parameters should be managed promptly and treatment modified before any further venetoclax/placebo is administered.

8.2.1.2 Week 1 Day 2 and Week 2 Day 2

Pre-dose

- AEs
- Concomitant medications (including chemotherapy, radiation, over-the-counter drugs, vitamins, and herbs)
- Vital signs
- Laboratory Tests
 - o Blood chemistry (creatinine, uric acid, potassium, phosphorus, calcium, and albumin, if available)

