- Risk of TLS is to be re-assessed prior to each venetoclax dose ramp-up. Administration of prophylaxes as needed is to occur within 72 hours of dosing. Subjects with high tumor burden at baseline may be hospitalized for a minimum of the first 24 hours of treatment (and up to 48 hours at the discretion of the investigator) at the start of the 20 mg (ramp-up dose) and the 50 mg dose levels and blood chemistry (creatinine, uric acid, potassium, phosphorus, calcium, and albumin, if available) should be monitored pre-dose and 4±1, 8±1, 12±1, 24±2 and as needed 48±2 hours after the venetoclax dose. Additionally, for high-risk TLS subjects, post-dose blood chemistries will be monitored at pre-dose and 6-8 hours after the venetoclax dose during ramp up of the 100 mg, 200 mg and 400 mg dose levels. For all other subjects, blood chemistry will be monitored pre-dose, 6-8 and 24±2 hours after the venetoclax dose at the 20 mg and the 50 mg dose levels.
- P PRO questionnaires (FACT-Lym, EQ-5D-5L) should be completed prior to any assessments, and before being clinically evaluated by the study nurse or physician. The questionnaires will be administered on Week 1 Day 1, Week 13 Day 1 (±7 days); every 4 weeks for the remainder of the 1st year; every 8 weeks during the 2nd and 3rd years; and every 12 weeks thereafter until disease progression.
- ^q Hematology includes complete blood count with differential and platelet counts.
- ^r Blood chemistry: Sodium, potassium, chloride, BUN, creatinine, glucose, calcium, total protein, albumin, AST, ALT, alkaline phosphatase, total bilirubin, LDH, phosphate, uric acid, urea, magnesium and bicarbonate. Serum creatinine, uric acid, potassium, phosphorus and calcium should be assessed within 72 hours prior to the 1st venetoclax dose and before each dose increase.
- ^s Urinalysis: pH, ketones, specific gravity, bilirubin, protein, blood, and glucose.
- Hepatitis C antibody, hepatitis B surface antigen and hepatitis B core antibody will be evaluated. If hepatitis B core antibody or hepatitis B surface antigen or Hepatitis C antibody is positive, then PCR to quantitate hepatitis B DNA or hepatitis C RNA must be performed. DNA PCR needs to be confirmed negative (< 29 U) prior to enrollment in subjects who are hepatitis B core antibody or hepatitis B surface antigen positive. For subjects who are hepatitis C antibody positive, hepatitis C PCR needs to be confirmed negative prior to enrollment.

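### The Appendix A and B footnotes make tumor lysis hospitalization at 20 and 50 mg optional and, like visit list 8.2.1.1, leave out subjects whose only risk factor is CrCl < 60 mL/min

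*Protocol*

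**What the plan says.** The rule itself is stated consistently. Protocol 3.1.2 has "subjects at increased risk of TLS will be hospitalized for a minimum of 24 hours", at the 20 mg step and again at the 50 mg step; 3.1.1 says the same for the Safety Run-in. For the treatment-naive arm, 3.1.3 has "Subjects in the protocol-defined increased-risk for tumor lysis syndrome (TLS) group will be hospitalized for a minimum of 24 hours", and 5.1.4 repeats it. Section 5.3.2.2 says that subjects with high tumor burden and/or CrCl below 60 mL/min "require hospitalization the first 24-48 hours of treatment at the 20 mg and the 50 mg ramp-up doses of venetoclax". Section 7.1.1.10 puts both criteria in one sentence: "Subjects with high tumor burden at baseline and/or CrCl < 60 mL/min will be hospitalized during the first 24-48 hours of treatment".

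The operational text differs. The footnote to the TLS Risk Assessment row in Appendix A reads "Subjects with high tumor burden at baseline may be hospitalized for a minimum of the first 24 hours of treatment", and Appendix B uses the same words. The footnote attaches the inpatient chemistry times to that group and continues: "For all other subjects, blood chemistry will be monitored pre-dose, 6-8 and 24±2 hours after the venetoclax dose". The pre-dose list in 8.2.1.1 has "Hospitalization of subjects with high tumor burden". Neither footnote nor this list item mentions creatinine clearance.

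On relaxing the rule, 5.3.2.2 says: "During the course of the study, the DMC will review unblinded TLS data to determine whether continued hospitalization of these subjects is warranted".

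**The concern.** Section 8.2 sends sites to Appendices A and B for the full set of procedures at each visit, so the footnote is working text rather than background. A site relying on it, or on 8.2.1.1, could keep a subject with reduced renal function and no bulky disease as an outpatient at the first two venetoclax doses. Section 5.3.2.2 itself states that reduced renal function adds to TLS risk. What is at stake is that the protocol's own safety rule is applied to everyone it was written for.

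**Working it through.** No power, alpha or event count enters. The check is a comparison of texts, followed by simple counting.

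**1. Does high tumor burden include renal function?** No. Sections 3.1.1 and 5.3.2.2 define it as a lesion > 10 cm, or a lesion > 5 cm with circulating lymphocytes > 25,000 cells/mm³. CrCl < 60 mL/min is a separate criterion joined by and/or, so it is sufficient alone.

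**2. Can a subject qualify on CrCl alone?** Yes. Sections 4.1.1 and 4.2.1 set the eligibility floor at 30 mL/min, so the group is CrCl 30 to < 60 mL/min without high tumor burden. The documents do not give its size.

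**3. The texts side by side (20 and 50 mg)**

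| Text | Obligation | Group named |
|---|---|---|
| 3.1.1, 3.1.2, 3.1.3, 5.1.4 | mandatory | increased risk (tumor burden and/or CrCl) |
| 5.3.2.2, 7.1.1.10 | mandatory | tumor burden and/or CrCl < 60 |
| Appendix A and B footnotes | optional (*may*) | tumor burden only |
| 8.2.1.1 | listed as a procedure | tumor burden only |

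**4. Consequence for a CrCl-only subject, footnote read alone**

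- Minimum inpatient time under the rule: 24 h × 2 steps = 48 h. Under the footnote: 0 h.
- Timed post-dose draws under the rule (4, 8, 12, 24 h; the as-needed 48 h draw excluded): 4 × 2 = 8. Under the footnote (6-8 h, 24 h): 2 × 2 = 4. The first draw moves from 4 h to 6-8 h.

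**5. Could DMC review explain the difference?** It could explain *may* for the Randomization Phase, where 3.1.2 gives admission as the initial position. It cannot explain the missing criterion, because 3.1.2 describes the review as covering high tumor burden and/or creatinine clearance below 60 mL/min. Nothing in either document reports a decision to relax the rule.

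**6. Related wording at the later steps.** The footnotes' sentence on 100, 200 and 400 mg refers to high-risk TLS subjects, a category the protocol does not define (it has low and increased). The 6-8 h line of 8.2.1.4 (weeks 3 to 5) names high tumor burden only, whereas 7.1.1.10 applies that draw to all increased-risk subjects. Separately, 5.3.2.2 asks outpatients for chemistry at 6-8 h and 24 h at every ramp-up dose, while 7.1.1.10 and the footnotes list only a 6-8 h draw at these three doses, for increased-risk subjects.

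**The case against.** The strongest reply is that a site is unlikely to be misled. The rule appears in six sections. Section 8.1.1 requires a determination of risk level and need for admission at screening. TLS category is a stratification factor for randomized subjects (5.1.2.1). Section 7.1.1.10 also refers to the medical monitor the admission of subjects otherwise considered at risk. These controls are real and are why the point is minor. They do not make the footnote correct.

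A reader might infer more than the documents support:

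- *That 8.2.1.1 makes admission optional.* It does not. It lists admission as a procedure; its only fault is the narrower group.
- *That the lost blood draws are a second harm.* Section 8.2.1.1 assigns draws by admission status, so they are lost only if the admission is missed.
- *That 7.1.1.10 and the footnotes contradict the 24-hour dosing hold of 5.3.2.2 at 100 to 400 mg.* They state no hold at any dose, including 20 and 50 mg, where 8.2.1.2 imposes one. Silence is not a conflict.
- *That sites should follow the stricter 5.3.2.2 chemistry schedule meanwhile.* That is a judgment for the sponsor. Appendices A and B have no Day 2 visit in weeks 3 to 5, so it would add next-day visits; and 7.1.1.10 already refers to 5.3.2.2 for TLS prophylaxis and management.

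Section 5.3.2.2 opens its admission sentence with a reference to investigator assessment, but its verb is still one of requirement.

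**Conclusion.** The Appendix A and B footnotes are wrong as written, in obligation and in population; 8.2.1.1 is wrong in population only. The group left out is CrCl 30 to < 60 mL/min without high tumor burden, at 2 of the 5 dose steps.

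Severity is minor. SAP Section 1 says that the treatment-naive cohort has completed enrollment, and SAP Section 4 reports randomization in the past tense. If enrollment is indeed closed, what remains is mainly repeat ramp-ups after an interruption (5.3.2.5) that restart at 20 or 50 mg within the 104-week venetoclax period. The documents do not say how many subjects that could involve. There is no effect on alpha, power or the between-arm comparison.

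The chemistry schedule at 100, 200 and 400 mg is a secondary question for the sponsor to clarify.

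**What to change.** Three corrections carry the point:

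- **Appendix A footnote:** name both criteria and make admission mandatory, as 7.1.1.10 does; for the Randomization Phase, subject to any DMC decision under 3.1.2.
- **Appendix B footnote:** the same, without an exception unless the sponsor confirms that the general DMC sentence in 5.3.2.2 covers that arm. Sections 3.1.3 and 5.1.4 contain none.
- **8.2.1.1:** extend the item to high tumor burden and/or CrCl < 60 mL/min.

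Two alignments belong with them: replace the high-risk label in the footnotes with increased-risk, and add CrCl < 60 mL/min to the 6-8 h line of 8.2.1.4. The sponsor should also state which chemistry schedule governs at 100, 200 and 400 mg, including whether the 24 h draw and low-risk subjects are covered.

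Section 12.14 routes protocol changes through an amendment with ethics approval, so the edits should go into the next one. The cost is a few lines of text, with no change to design or analysis.

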8.3.1 Response Follow-up

Subjects who discontinue treatment for reasons other than PD will participate in the response follow-up. From the time of first dose (Safety Run-in Period and TN open-label arm) or randomization (for Randomization Phase), these subjects will be followed every 12 weeks for the first year; every 16 weeks during the second and third years; and every 24 weeks thereafter until PD. Once subjects progress (for subjects who have not withdrawn consent), they will start the Long-term Follow-up.

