8.3.2 Long-term Follow-up

Subjects in Long-term Follow-up will be contacted approximately every 12 weeks (±14 days) by clinic visit or telephone to assess survival and the use of alternative anticancer therapy. Subjects will be contacted until death, subject withdrawal, or study termination by the Sponsor, whichever occurs first.

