11.4.5 Other Malignancies

All new malignant tumors including solid tumors, skin malignancies and hematologic malignancies will be reported for the duration of study treatment and during any protocol-specified follow-up periods including post-progression follow-up for OS. If observed, enter data in the corresponding eCRF.

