14 APPENDICES

Appendix A. Schedule of Assessments – Standard Ramp-up Schedule

	Week		1			2		3	4	5	6	8	10	Week 13	Response	EOT°	RFUd	LTFUw
	Day	1	2	3	1	2	3	1	1	1	1	1 (±1 day)	1 (±1 day)	& beyonda (±7 days)	Assessment ^b (±7 days)	(±7 days)	(±14	days)
						1	Stu	ıdy Drug	Adminis	tra	tion			(
Ibrutinib 560 mg daily										Co	ntin	uous						
Venetoclax daily dose / place	ebo	2	20m	g		50r	ng	100mg	200mg			400)mg con	tinuous targ	et daily dose			
Procedure	Screening Day -28 to -1																	
Informed consent	X																	
Medical history/demographic/prior treatment	X	X																
Confirm eligibility	X	X																
Concomitant medications ^e	X	X	X	X	X	X	X	X	X	X	X	X	X	X		X		
AEsf	X	X	X	X	X	X	X	X	X	X	X	X	X	X		X		
Physical exam ^g	X	X			X			X	X	X	X	X	X	X		X		
Vital signs h	X	X	X		X	X		X	X	X	X	X	X	X		X		
ECOG	X	X						X			X			X				
ECGi	X															X		
Disease Assessment																		
CT/PET/MRI/endoscopy ⁱ	X														X		X	
Tumor tissue ^k	X														(X)			
Bone marrow biopsy ^x	X														(X)			
B-symptoms	X														X		X	
Overall response assessment ^m															X		X	
MRD Bone marrow aspirate ¹	X														(X)			
MRD assessment in blood ⁿ		X													X	X		
TLS Risk Assessment ^o	X	X	X	X	X	X	X	X	X	X	X	X	X	X				
PROp		X												X				
Medical resource utilization (MRU)		Н	ospit	aliza	tions	, em	ergency	departm				oietic gr ent perio		tor use to be	documented thro	oughout		
Biomarker Bone marrow Aspirate ^l	X														(X)			
Biomarker Peripheral Blood ^u		X													X	X	X	

	Week		1			2		3	4	5	6	8	10	Week 13	Response	EOTe	RFU ^d	LTFU
	Day	1	2	3	1	2	3	1	1	1	1	1 (±1 day)	1 (±1 day)	beyond ^a (±7 days)	Assessment ^b (±7 (±7 days) days)		(±14 days)	
			•	•			Stu	ıdy Druş	Adminis	tra	tion					•	•	
Ibrutinib 560 mg daily										C	ntir	uous						
Venetoclax daily dose / place	bo		20mg	3		50n	ng	100mg	200mg			400)mg con	tinuous targ	et daily dose			
Procedure	Screening Day -28 to -1																	
Hematology ^q	X	X			X			X	X	Х	X	X	X	X	X	X		
Blood chemistry ^r	X	X	X	X	X	X	X	X	X	X	X	X	X	X		X		
Urinalysis ^s	X															X		
Serum or Urine Pregnancy	X	X														X		
Hepatitis serologies ^t	X																	
Coagulation panel	X																	
Buccal Swab		X																
Serum β ₂ -microglobulin	X																	
PK blood sampling ^v											X							
Survival status, incl. other malignancies ^w																		X
Subsequent Anticancer Therapy																	X	X

Abbreviations:

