- ^u Blood biomarker samples will be drawn at baseline, at documented complete response and onwards every 12 weeks (±7 days) for the remainder of the 1st year; every 16 weeks during the 2nd and 3rd years; and every 24 weeks thereafter until PD.
- V PK samples will be drawn at protocol-specified timepoints: pre-dose (30min), 1hr (±15min), 2hrs (±15min), 4hrs (±30min), 6hrs (±30min), and 8hrs (±1hr) post dose.
- W After progression, survival status, other malignancies and subsequent anticancer therapy will be collected approximately every 12 weeks (based on Week 1 Day 1 for a subject) until death, withdrawal by subject, loss to follow-up, or study terminated by Sponsor, whichever comes first.
- A unilateral bone marrow biopsy will be done at Screening or up to 28 days before the 1st administration of study drug for standard pathology. A 2nd bone marrow biopsy will be performed in subjects with positive bone marrow involvement at baseline by standard pathology who achieve a CR.

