5 SAFETY ASSESSMENTS

Safety data will be summarized by treatment arm based on the Safety Population.

Adverse events (AEs) will be coded in accordance with the Medical Dictionary for Regulatory Activities (MedDRA 24.1). Severity of AEs will be graded by the investigator according to the National Cancer Institute's Common Terminology Criteria for Adverse Events (NCI-CTCAE), Version 4.03.

The treatment-emergent period is defined as the period of time from the date of the first dose of study treatment up to 30 days after the date of the last dose of study treatment or the day before initiation of subsequent anti-cancer treatment, whichever comes first.

Treatment-emergent adverse events (TEAEs) are those events that occur or worsen during the treatment-emergent period or that are related to the study treatment.

Adverse Events of Special interest (AESI)as listed below will be summarized by treatment arm:

- Protocol-defined events of clinical interest including hemorrhagic events and major hemorrhage.
- Other safety observations including other malignancies (including NMSC, NSC, and MSC), hypertension ("Hypertension" SMQ narrow), interstitial lung disease ("Interstitial lung disease" SMQ narrow), atrial fibrillation (PT = "atrial fibrillation"), cardiac arrhythmia ("Cardiac arrhythmias SMQ, excluding PT of "atrial fibrillation"), Cardiac failure, ventricular tachyarrhythmia ("Ventricular Tachyarrhythmia" SMQ narrow), tumor lysis syndrome ("Tumour lysis syndrome" SMQ narrow), ischemic stroke ("Ischaemic central nervous system vascular conditions" SMQ narrow), sepsis (PTs = "Sepsis", "Bacteraemia", "Fungaemia" or "Septic" (excluding "Septic screen")), cytopenias (PTs="Anemia", "Neutropenia", "Febrile Neutropenia", and "Thrombocytopenia"), infections including viral reactivation (SOC = "Infection and Infestations"), hepatic disorders (SOC = "Hepatobiliary disorders"), embryo-fetal toxicity (SOC = "Pregnancy, puerperium and perinatal conditions"), Diarrhea (PT = "Diarrhoea")

All laboratory values will be converted to and reported as international standard (SI) units. Data for hematology and biochemistry were collected at the respective local laboratories and will be summarized and analyzed by treatment arm. Laboratory parameters will be graded using the NCI CTCAE, Version 4.03. Unless otherwise specified, only baseline and post-baseline values collected during the treatment-emergent period will be included in the safety analysis.

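### Protocol 11.4.5 requires new malignancies to be reported in every follow-up period, but Appendices A and B schedule their collection only after progression, and SAP Section 5 sets no analysis window for late ones

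*Protocol*

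**What the plan says.** **Reporting duty.** Protocol Section 11.4.5 says that all new malignant tumors, skin cancers included, "will be reported for the duration of study treatment and during any protocol-specified follow-up periods including post-progression follow-up for OS", and adds: "If observed, enter data in the corresponding eCRF".

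**Follow-up periods.** Section 8.3 has two. On the first, Section 8.3.1 says: "Subjects who discontinue treatment for reasons other than PD will participate in the response follow-up". The visits run "every 12 weeks for the first year; every 16 weeks during the second and third years; and every 24 weeks thereafter until PD". LTFU begins once a subject progresses. Section 8.3.2 describes its contacts as being made "to assess survival and the use of alternative anticancer therapy" and does not name malignancies.

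**Schedules.** In Appendix A (run-in and randomized subjects) and Appendix B (treatment-naive arm), the row "Survival status, incl. other malignancies" is marked only in the LTFU column. Footnote w, attached to that row, says: "After progression, survival status, other malignancies and subsequent anticancer therapy will be collected approximately every 12 weeks". The adverse event row ends at the End-of-Treatment visit.

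**Adverse event window.** Section 11.4.2 collects adverse events to 30 days after the last dose. Later serious events are to be reported if considered related to study drug.

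**SAP.** Section 5 defines a treatment-emergent period ending 30 days after the last dose, or the day before subsequent anti-cancer treatment if that is sooner. Its list of events of special interest then includes "Other safety observations including other malignancies (including NMSC, NSC, and MSC"), with no window of its own.

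**The concern.** Section 11.4.5 and the schedules describe different collection periods for the same item. Sites work from the schedule and the eCRF pages tied to it, so an item with no mark at a visit depends on someone remembering a rule stated elsewhere.

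New cancers are a harm that can appear late, and non-melanoma skin cancer is a named ibrutinib risk (Section 1.2.4.8). The subjects affected are those who stopped all study drug without progressing. They may stop for toxicity, by withdrawing from treatment but not from follow-up, or on the investigator's decision. If that group differs in size or follow-up between arms, unprompted recording makes the comparison of second cancers less even than the rest of the safety data.

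The SAP adds a second gap. Even when a late cancer is recorded as 11.4.5 asks, Section 5 does not say whether it enters the by-arm table, so two programmers could produce different counts from the same data.

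**Working it through.** The plan states no figure on this point, so the check sets the sections side by side.

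1. **Is RFU covered by 11.4.5?** Yes. The duty extends to any follow-up period specified in the protocol, with post-progression follow-up given as one included case. RFU is specified in Section 8.3.1 and precedes progression.

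2. **What is marked under RFU?** In both appendices: imaging and endoscopy, B-symptoms, overall response, biomarker blood and subsequent anticancer therapy. Adverse events and other malignancies are not marked.

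3. **Is this only a matter of layout?** Probably not. The next row, subsequent anticancer therapy, is marked under both RFU and LTFU, so the table does distinguish the two columns.

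4. **Coverage by period:**

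| Period | Required by 11.4.5 | Scheduled collection |
|---|---|---|
| First dose to 30 days after last dose | Yes | Yes, through adverse event reporting |
| More than 30 days after last dose, before PD (RFU) | Yes | None; related serious events remain reportable under 11.4.2 |
| After PD (LTFU) | Yes | Yes, about every 12 weeks (footnote w) |

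The gap is the middle row.

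5. **How long can it last for one subject?** Take a hypothetical subject whose last dose is at Week 25 (Day 169 in the imaging table of SAP Appendix 8.1) and who has not progressed by Week 145 (Day 1009). Adverse event collection ends at Day 169 + 30 = Day 199. The uncovered time is 1009 − 199 = 810 days, or 810/365.25 = about 2.2 years. RFU visits in that time fall at Weeks 37, 49, 65, 81, 97, 113, 129 and 145: eight visits, none with a malignancy item. If the subject dies or the study closes before PD, LTFU never starts and no scheduled query is ever made off drug.

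6. **SAP window.** Section 5 offers one event window, the treatment-emergent period, and its definition of a treatment-emergent event also admits related events outside that period. For other malignancies it states neither a restriction to that window nor an extension beyond it. Table 3 of the SAP adds nothing on timing.

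**The case against.** The best defence is that 11.4.5 is binding by itself. A site that sees a new cancer during RFU must record it, schedule mark or not. RFU visits bring imaging, a response assessment and a question on subsequent therapy, so the subject is being seen. Related serious events stay reportable after day 30, and a cancer that arose during RFU could still be entered at LTFU once the subject progresses. All of this stands.

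Three stronger readings are tempting, and the documents do not support them:

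- **That these cancers are lost.** The duty in 11.4.5 remains. What is absent is a prompt, so the supportable claim is possible under-ascertainment.
- **That the bias favors the combination.** Nothing shows more discontinuation of all study drug without PD on that arm. Section 5.4 lets a subject who stops one drug for tolerability continue on the other, and SAP Section 2 dates the last dose by the later drug. A subject who stops only venetoclax therefore remains under adverse event collection and outside the gap.
- **That the SAP counts only treatment-emergent malignancies.** It does not say so. Section 5 states such a restriction in its laboratory paragraph but not for this list.

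The defence does not remove the mismatch. Unprompted reporting is weaker than a scheduled item, late non-serious cancers fall outside 11.4.2, and retrospective entry at LTFU is possible only for subjects who progress.

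**Conclusion.** The inconsistency is real and limited in extent. It concerns subjects who stop all study drug for any reason other than PD, from more than 30 days after the last dose until PD. It appears in both schedules and so affects the run-in, the randomized phase and the treatment-naive arm. Cancers on treatment, within 30 days of the last dose, or after progression have scheduled collection.

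The number of cancers affected cannot be derived. The documents give no rate of discontinuation without PD, no progression-free time after such discontinuation and no background cancer rate, and some cancers will be reported without a prompt. Unequal ascertainment between arms is conditional on unequal discontinuation, and its direction is unknown. The SAP point is an omission: the window for later malignancies is unstated. Neither point touches the primary PFS analysis.

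**What to change.** - **Appendices A and B:** mark other malignancies in the RFU column, collected at the RFU visits already planned (every 12, then 16, then 24 weeks).
- **Footnote w:** keep the interval of about 12 weeks for post-progression LTFU only, and add that before progression the item follows the RFU visits. Simply moving the start of the footnote to the end of treatment would impose 12-weekly contacts in periods when RFU runs every 16 or 24 weeks.
- **Sections 8.3.1 and 8.3.2:** name other malignancies in both, so that the text agrees with 11.4.5 and the schedules.
- **SAP Section 5:** state that other malignancies are summarized by arm from first dose through all follow-up, with treatment-emergent events shown separately.

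The cost is one added question at visits that already take place, on the eCRF that 11.4.5 already refers to, and one added table. The change affects data collection and reporting only.
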